Those patients who experience a Serious Adverse Event (SAE) suspected of being related to the study drug during the treatment period will be asked to provide a single pharmacokinetic (PK) blood sample at discretion of the clinician. Ideally this should be drawn before the drug is taken that day. The sample may still be taken if the patient has taken their study drug within 1.5 hours of the PK blood draw. If it has been longer than 1.5 hours since the study medication was taken, the PK draw should be postponed until the next morning; however, if a draw the next day is not possible, then the blood sample may be collected and timing noted on the accompanying paperwork to the lab. All samples will be processed by a central laboratory.

Risk Mitigation and Alternative Strategies

We have structured the study to minimize risk to the subjects and have included ways to assess, track, and mitigate these potential risks. We will use a dosing scheme that has been shown convincingly to be safe and well tolerated. We will include a lead-in dosing period with testing for drug-induced hematuria during the early part of the study despite the fact that this adverse event has only been demonstrated to occur at higher doses. During clinical trials, the one serious adverse event reported was in a subject with Gilbert syndrome, a genetic disease characterized by a drastic reduction in the activity of UGT1A1. As VC is known to be a moderate inhibitor of UGT1A1, patients with Gilbert syndrome are excluded from this study.

We have included liver function testing to monitor general liver health and to indicate potential hepatobiliary issues. Frequent assessments of general health will be performed and subjects will be instructed to alert the study coordinator of any potentially drug-related complications, particularly abdominal pain. Standard drug discontinuation criteria will be included in the protocol based on the investigators' knowledge of PSC and PSC- related clinical trials, information derived from previous vidofludimus clinical trials, and the extensive data contained within the drug manufacturer's

Investigator's Brochure.

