Biliary hyperplasia, or increased cell proliferation in bile ducts, was seen when VC was tested in dog and rat models. In humans, there is no clinical means to test for this effect. When VC was stopped in either animal the bile duct cell proliferation stopped. This side-effect, which was only visible under the microscope, was only seen when the blood levels of VC were significantly higher than what we anticipate in human subjects who enter this clinical trial.

2. Risks related to the disease to be studied (PSC either in the absence or the presence of IBD)

Potential problems that may occur during the clinical trial as part of the natural course of PSC and/or PSC- associated IBD include problems related to PSC biliary strictures. Most PSC patients have strictures in the biliary tree. Dominant strictures can induce stagnation of bile, resulting in bacterial colonization and secondary bacterial cholangitis. This biliary infection, acute ascending cholangitis, is a gastrointestinal emergency with high mortality rates if left untreated. The management is directed at treating the infection with broad-spectrum antibiotics and biliary drainage (endoscopic, percutaneous, or surgical).

Cholangiocarcinoma is a feared complication of PSC. Annual cross-sectional imaging of the liver is currently recommended as standard of care for all PSC patients to screen for cholangiocarcinoma. We recommend liver ultrasound every 6-12 months in all PSC patients. Magnetic resonance imaging of liver (liver MRI) is permissible, but not required.

PSC is often associated with inflammatory bowel diseases, namely ulcerative colitis. Study subjects will undergo clinical assessment for IBD at clinic visits. Study subjects will be instructed to call the study coordinators/investigators to report any new symptoms that may be due to flare up of IBD. Common symptoms that suggest IBD flare up are abdominal pain, fever, bloody stools, and an increase in frequency of bowel movements. In addition, phone monitoring will be performed periodically throughout the study to specifically inquire about the presence of any of these

symptoms. If symptoms are reported, the clinical site investigator may request further diagnostic testing and a clinical evaluation will be required. As symptoms of *Clostridium difficile* colitis may resemble those of an IBD flare-up, *Clostridium difficile* infection needs to be ruled out.

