Risks associated with the use of VC include hematuria early in the course of treatment, believed to be due to microcrystallization of excess uric acid in the urine. As a precaution against this risk, patients with serum uric acid levels >1.2 ULN will be excluded from the study. Additionally, study subjects will be advised to drink sufficient fluids during the study to ensure adequate urine flow. Further, the trial will include a one week lead-in period where subjects receive half the treatment dose to minimize the risk of drug intolerance during the initial treatment period. Subjects will be monitored for two weeks after initial drug exposure for elevated RBCs in the urine by a urine dipstick test. It is not anticipated that hematuria will be seen if it has not developed within the first two weeks of drug exposure. Positive results will be immediately reported to the study coordinator and standard medical care will be provided. Three consecutive positive readings will require microscopic assessment of urine for sediment. All findings of RBCs in the urine will be listed as urinalysis abnormalities but will only be recorded as an adverse event when deemed by the investigator to be clinically significant. The investigator will assess whether there are more probable alternatives to explain this finding (e.g. evidence of contamination, evidence of infection not considered secondary to a drug induced damage, other benign causes such as menstruation, vigorous exercise, viral illness, trauma, or infection). If moderate or severe hematuria (see Table 4) cannot be remedied, the subject will discontinue VC treatment.

Due to an occurrence of a potentially drug-related adverse event of hepatitis in a subject with Gilbert syndrome, patients with known or suspected Gilbert syndrome or with elevation of indirect (unconjugated) bilirubin above 1.2 ULN will be excluded from this clinical study

To protect pregnant women, fetuses, and breastfeeding children, women who are pregnant, attempting to become pregnant, or breastfeeding will be excluded from the study. For female subjects of childbearing age, some form of contraception will be required during the study. A urine pregnancy test will be performed during each clinic visit and once a month during the entire treatment period. Subjects with a positive pregnancy test will discontinue the study immediately.

Classification	Symptoms
Mild	Asymptomatic hematuria: clinical or diagnostic observations only

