Cholangiocarcinoma (CCA) is one of the most serious complications of PSC. Screening for CCA is currently recommended every 6-12 months (by liver ultrasound or MRI) as part of standard of care for PSC patients. Patients with CCA at screening will be excluded. If during the course of the study CCA is suspected, subjects will undergo the necessary evaluations (which is part of standard of care) to exclude CCA.

As PSC is frequently associated with IBD, study subjects will undergo clinical assessment for IBD at clinic visits and by phone between these visits. Study subjects should report any new symptoms of an IBD flare to the study coordinator. These symptoms include abdominal pain, fever, bloody stools, and an increase in frequency of bowel movements.

In subjects with UC, we will use the Ulcerative Colitis Clinical Score to assess the disease activity/severity. This score, a modification of the well-known Mayo Score, consists of 4 items: stool frequency, rectal bleeding, subject's functional assessment, and physician's global assessment (PGA). Scores range from 0 to 12 points, with higher scores meaning more active disease. The Short inflammatory Bowel Disease Questionnaire (SIBDQ) is a health-related quality of life HRQoL tool measuring physical, social, and emotional status in IBD patients. The SIBDQ contains 10 items with 4 dimensions: bowel symptoms (3 items); systemic symptoms (2 items); emotional function (3 items); and social function (2 items). The total score ranges from 10 (worst health) to 70 (best). The SIBDQ can be administered and scored quickly and easily.

In cases of confirmed *Clostridium difficile* colitis, any antibiotics the patient is already taking that are not specifically directed at *Clostridium difficile* will be reduced or stopped. Antibiotics such as vancomycin or other appropriate antibiotics specifically directed at *Clostridium difficile* will be administered. The use of immunosuppressive drugs should be minimized, but if required, patient will be closely monitored.

IBD, particularly ulcerative colitis, is an important risk factor for colorectal cancer. Currently, screening colonoscopy is recommended annually in patients with PSC and IBD.

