The protections against risks related to subject confidentiality are outlined in the *Protection of Human Subjects* section. Briefly, the study protocol, documentation, data, and all other information generated will be held in strict confidence, with only authorized personnel permitted access. Study data and records will be stored securely in a password-protected database or in locked cabinets in locked offices. Study subjects, their samples, and their data will be labeled using only unique study identification numbers. Names and identifiers of study subjects will be coded and if data from the study are published or presented publicly, a subject's identity will be kept strictly confidential.

To ensure the safety of the participants and the validity and the integrity of the data, the clinical trial will be monitored by an independent DSMB with experience in clinical trials in liver diseases, including cholestatic liver diseases. They will act as the designated safety officers for the trial, reviewing clinical trial reports every 6 months and addressing all reports of AEs. Acting independently of the PI, they will monitor study progress, protocol adherence, IRB compliance, and adherence to the proposed protections against risks related to subject confidentiality.

A safety monitoring system will be used to ensure appropriate identification, tracking and reporting of adverse events (AEs). We will use the Common Terminology Criteria for Adverse Events (CTCAE) grading system to monitor the clinical trial's potential AEs and to grade the severity of any AEs that may occur. The CTCAE is a descriptive terminology that can be utilized for adverse event reporting. A grading scale based on severity is provided for each AE term. The CTCAE displays grades 1 through 5 with unique clinical descriptions of severity for each AE based on the general guideline shown in Table 6.

Grade	Description
1	Mild; asymptomatic or mild symptoms; clinical or diagnostic observations only; intervention not indicated.

2	Moderate; minimal, local or noninvasive intervention indicated; limiting age - appropriate instrumental activities of daily living (ADL).
3	Severe or medically significant but not immediately life threatening; hospitalization or prolongation of hospitalization is indicated; disabling; limiting self-care ADL.
4	Life-threatening consequences; urgent intervention indicated.
5	Death related to AE.

Table 6. CTCAE grading system developed by the National Cancer Institute

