The occurrence of an AE, serious AE (SAE), or unanticipated problem may come to the attention of study personnel during study visits, interviews of a study subject presenting for medical care unrelated to this study, telephone calls, laboratory test review, and/or upon review of study reports by the study monitor. An SAE is defined by the FDA as “an adverse event that, in view of the investigator, study coordinator, or the sponsor, results in any of the following: death, a life-threatening adverse event, inpatient hospitalization or prolongation of existing hospitalization, a persistent or significant incapacity or substantial disruption of the ability to conduct normal life functions, or a congenital anomaly/birth defect”. All AEs will be captured and documented. Information collected about the AEs will include time of onset, nature, severity, relationship to the study drug, related to the natural history of PSC/IBD, subject hospitalized or not, intervention(s), time of resolution of resolution/stabilization, and outcomes.

Safety-related information (of any level) will be entered into the clinical database and reviewed routinely. All AEs, SAEs, and unanticipated problems will be managed in a manner consistent with local IRB guidelines. We will use the following strategy when reporting all AEs (regardless of severity and relationship to study drug or natural course of PSC/IBD):

1. If the AE(s) meet the criteria for study termination the clinical trial will be stopped immediately until further discussion with the sponsor.
2. For all other AEs and unanticipated problems, reports will be made within 72 hours to the clinical trial monitor and/or local IRB. The clinical trial monitor/IRB will assume the responsibility for reviewing the clinical trial data for safety concerns and reporting to any appropriate regulatory bodies including the sponsor.

The trial shall be stopped until further discussion with the sponsor if any of the following occur:

- 3 subjects develop the same grade 3 CTCAE
- 2 subjects develop any grade 4 CTCAE
- 1 subject develops a grade 5 CTCAE

Participation of individual study subjects shall be terminated if any of the following occur:

- Elevated ALP $\geq 3 \times$ baseline that does not return to within 10% of baseline within two weeks
- Elevated AST and/or ALT $\geq 3 \times$ baseline that does not return to within 10% of baseline within two weeks

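### The SAE definition has no important-medical-event criterion, so outpatient malignancy or liver injury may go uncounted as serious; separately, no procedure follows a pregnancy to its outcome

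*Combined protocol and SAP*

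**What the plan says.** **SAE definition (Data and Safety Monitoring Plan).** As judged by the investigator, coordinator or sponsor, an SAE is an event that "results in any of the following: death, a life-threatening adverse event, inpatient hospitalization or prolongation of existing hospitalization". The list then adds lasting incapacity or disruption of normal life, and birth defect, and stops there.

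**AE handling (same section).** "All AEs will be captured and documented", with severity, relationship, hospitalization and outcome recorded. Reports are due within 72 hours whatever the severity or relationship. The trial-level stopping rules use CTCAE grade. Table 6 describes grade 3 as "Severe or medically significant but not immediately life threatening", but the text does not connect that grade to seriousness.

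**PK sample (Pharmacokinetic Sample; Table 3).** One sample, at the clinician's discretion, is requested from "Those patients who experience a Serious Adverse Event (SAE) suspected of being related to the study drug during the treatment period". Table 3 repeats the SAE condition and adds that the sample is taken if possible.

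**Events of special interest.** Table 5 requires drug interruption and work-up for several ALT and bilirubin patterns, without saying whether these are SAEs. Table 7 lists cholangiocarcinoma and colon cancer as expected AEs. Section II(b)2 says "Cholangiocarcinoma (CCA) is one of the most serious complications of PSC" and provides for standard-of-care evaluation, again with no seriousness rule.

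**Pregnancy.** Section II(b)1 says "Subjects with a positive pregnancy test will discontinue the study immediately". Timeline and Schedule and the individual termination criteria agree. All subjects have a follow-up assessment at 30 days.

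**The concern.** Safety is part of the study's stated goal, and the safety output in the Statistical Analysis Plan paragraph is the incidence, type and relatedness of SAEs and AEs. If the seriousness definition omits important medical events, whether an outpatient cholangiocarcinoma or a marked liver signal enters the SAE tally depends on how each investigator reads the life-threatening and incapacity criteria. Two sites could classify the same event differently.

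Liver injury matters most. The protocol reports that the one SAE in earlier vidofludimus trials was hepatitis, in a subject with Gilbert syndrome, and that UGT1A1 inhibition by the drug may have contributed. A drug level at the time of a suspected drug-related liver injury would be informative, yet the only PK request in the protocol depends on SAE status.

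Pregnancy is a separate gap. The definition names an outcome that can become known only months after the study has stopped contacting the subject.

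**Working it through.** The main check is textual: each event is taken through the rules that would classify it and trigger further data.

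1. **Is there an important-medical-event criterion?** The SAE list has five elements: death, life-threatening event, admission or prolonged admission, incapacity or disruption, and birth defect. The only similar wording is in Table 6, grade 3, which grades severity and is not tied to the SAE definition. So there is none.

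2. **Table 5 liver injury managed as an outpatient.** Example: ALT at least 3 x ULN with total bilirubin at least 2 x baseline, which interrupts study drug.
 - Admission criterion: not met.
 - Life-threatening or incapacity: met only if so judged.
 - Table 5: silent on seriousness.
 - Result: AE yes, SAE uncertain. Without SAE status there is no PK request, even if the injury is suspected to be drug-related.

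3. **New malignancy diagnosed as an outpatient.** The classification reasoning is the same: AE yes, SAE uncertain. A PK consequence follows only if the event is also suspected to be drug-related and arises during treatment, so it is doubtful here.

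4. **Birth defect.** It is in the definition. The subject leaves the study on a confirmed positive test, the last described contact is at 30 days, and no pregnancy or infant follow-up is specified. The category exists without a procedure to observe it. The PK sample is irrelevant, because it is limited to the treatment period and a birth outcome comes later.

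5. **Do the stopping rules compensate?** They require three subjects with the same grade 3 event, two with any grade 4, or one grade 5. A single grade 3 liver injury or malignancy triggers none of them, and none requests a drug level.

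6. **When would a PK sample have to be drawn?** In its interruption rows, Table 5 repeats blood tests 2 to 5 days later. The half-life is given as about 30 h (Significance) and about 36 h (Section I(a)). Assuming single-exponential decline and no dosing after interruption, the fraction of the level remaining at time t is 2^(-t/half-life):

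| Time since interruption | Half-life 30 h | Half-life 36 h |
|---|---|---|
| 48 h | 2^(-1.60) = 33% | 2^(-1.33) = 40% |
| 120 h | 2^(-4.00) = 6% | 2^(-3.33) = 10% |

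A tube added to the repeat test would mostly measure washout. The existing PK instructions aim for a draw before that day's dose or within 1.5 hours after it. A useful sample after interruption therefore needs an early draw and a recorded time since last dose.

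**The case against.** The strongest reply is that little is lost. All AEs are captured, graded and reported within 72 hours, the DSMB addresses all AE reports, the stopping rules do not use SAE status, and AEs are tabulated alongside SAEs. The definition also applies in the investigator's view, and the protocol itself describes cholangiocarcinoma as carrying a grave prognosis, so an investigator could well call it serious. All of this stands. It limits the loss to the SAE label and the PK request, but supplies neither a seriousness rule nor a PK trigger for outpatient liver injury.

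Stronger readings that the documents do not support:

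- *That these events escape safety reporting.* They remain in the AE data.
- *That no exposure data would exist for liver injury.* Hospitalized cases suspected to be drug-related still qualify for the PK request, which is in any case discretionary.
- *That birth defects fall outside the definition or are lost to PK sampling.* They are listed, and the PK sample could not apply to them. Nor does anything bar recording an outcome that happens to be reported.
- *That the animal data make malignancy a demonstrated drug risk.* The protocol states "Biliary hyperplasia, or increased cell proliferation in bile ducts, was seen when VC was tested in dog and rat models", but adds that proliferation stopped on withdrawal and occurred only at blood levels well above those anticipated here.
- *That every Table 5 interruption should be an SAE.* Table 5 counts new or worsening pruritus among its symptoms, and the protocol describes strictures and cholangitis as part of PSC's natural course. A blanket rule could put disease fluctuation into the SAE count.
- *That the plan misstates the FDA definition it cites.* This cannot be checked from the documents and is not relied on.

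**Conclusion.** The point holds in a limited form. The SAE list has no important-medical-event criterion, so an outpatient malignancy or Table 5 liver injury may not be counted as serious, and a suspected drug-related liver injury managed as an outpatient may produce no PK request. Independently, the protocol names birth defect as an SAE but has no procedure to learn a pregnancy's outcome.

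The size is not usefully expressed as a number. The documents give no expected count of such events, and no SAE-rate threshold drives a decision. Pregnancy should be rare given the contraception requirement. The primary ALP analysis is unaffected. The matter deserves correction because safety is a stated aim and the remedy is cheap.

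The conclusion assumes that the definition is applied as written and that no separate manual or DSMB charter supplies a wider one. The PK timing figures also assume that the stated half-lives hold in subjects with liver injury. Slower elimination would leave more drug at the repeat test.

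**What to change.** 1. **SAE definition (Data and Safety Monitoring Plan).** Add *or an important medical event, in the investigator's judgment*. Name new malignancy and suspected drug-induced liver injury as examples to be assessed against the criterion. Do not make every Table 5 interruption an automatic SAE.

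2. **Pharmacokinetic Sample and Table 3.** Extend the discretionary request to Table 5 interruptions suspected to be drug-related. Ask for the draw as soon as possible, with time since last dose recorded, and do not wait for the 2 to 5 day repeat.

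3. **Pregnancy (Timeline and Schedule, Section II(b)1, individual termination criteria).** Leave the treatment withdrawal rule as written, and add safety contact until the pregnancy outcome is known.

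The cost is wording changes, an occasional extra PK tube, possibly a separate early draw, and rare additional phone contacts. The reported SAE count may be somewhat higher. Dosing, interruption and restart rules are untouched.

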Overall, the safety profile at the dosage level to be used in this trial is quite positive. An in-depth analysis of the entire clinical database demonstrates that vidofludimus at daily doses below 70 mg is not associated with an increased rate of clinically relevant adverse reactions, including hematuria, relative to placebo. These studies include 233 subjects with rheumatoid arthritis, Crohn's disease, or ulcerative colitis who received daily doses of vidofludimus 20 mg (~3000 treatment days) or vidofludimus 35 mg (~16,500 treatment days) in 3 clinical trials with individual treatment durations of 12-13 weeks.

The investigator will open an IND for the proposed clinical trial. Immunic AG, the drug supplier, will allow the investigator to reference Immunic's IND for vidofludimus calcium (see Letter of Support from Immunic).

2. Protections against risks related to the disease to be studied (PSC either in the absence or the presence of IBD): Acute ascending cholangitis, an acute biliary infection with high mortality rates, is a risk in patients with PSC. Study subjects will be asked about symptoms/signs of ascending cholangitis during clinic visits and phone calls, and subjects will be provided with a list of symptoms and instructed to report the symptoms to the study coordinator immediately if they arise. Symptoms suggestive of acute ascending cholangitis or biliary tree stricture include new onset jaundice, abdominal pain, dark urine, and light-colored stools. Study subjects will be advised to come to the clinic for evaluation or visit the nearest emergency room for consultation with an emergency room physician. If clinical suspicion for acute ascending cholangitis is high, the course of action may include aggressive antibiotic therapy and relief of biliary obstruction (via percutaneous, endoscopic, or surgical intervention), with or without a hospital stay. The Tokyo guidelines are commonly used for the diagnosis of acute ascending cholangitis.

The Tokyo criteria are:

- i. Two of three (fever, right upper quadrant pain, and jaundice), plus
- ii. Systemic inflammation (elevated white blood count and/or C-reactive protein), plus
- iii. Abnormal liver function tests, plus

iv. Imaging detection of biliary dilatation and etiology (stone, stricture, stent, neoplasm)

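### Minor: read literally at worst grade, the trial-halting rule pauses for three grade 3 cases of one event but not for two grade 3 cases plus one grade 4

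*Combined protocol and SAP*

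**What the plan says.** The Data and Safety Monitoring Plan gives three halting criteria, any one of which is enough: "The trial shall be stopped until further discussion with the sponsor if any of the following occur". They are:

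- "3 subjects develop the same grade 3 CTCAE"
- "2 subjects develop any grade 4 CTCAE"
- "1 subject develops a grade 5 CTCAE"

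Table 6 of the same section ranks the grades: grade 3 is severe but not immediately life-threatening, grade 4 is life-threatening, and grade 5 is death. The protocol does not say whether a grade 4 case also counts towards the grade 3 tally, or whether a subject is counted at worst grade or at every grade reached. The criteria carry no condition on relatedness to the drug.

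Events that do not meet the criteria go down a second path: "For all other AEs and unanticipated problems, reports will be made within 72 hours to the clinical trial monitor and/or local IRB". The plan adds that "The clinical trial monitor/IRB will assume the responsibility for reviewing the clinical trial data for safety concerns" and for reporting to the sponsor. The DSMB's task is described as "reviewing clinical trial reports every 6 months and addressing all reports of AEs".

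**The concern.** A halting rule should never be easier to trigger with a milder set of events than with a worse one. As written, this rule can be. Three subjects with grade 3 acute cholangitis stop the trial. If one of the three is life-threatening instead, the first criterion has two cases, the second has one, and neither is met.

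Such a mix of grades is plausible. Acute ascending cholangitis is a listed expected event (Table 7), and the protocol describes it as an emergency with high mortality if untreated. Disease-related events count towards the criteria as well as drug-related ones.

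Detection is not at stake, because the cluster is still reported and reviewed. What is lost is the automatic stop pending discussion with the sponsor, so dosing continues by default while others decide. The individual discontinuation rules for liver tests still apply, but no equivalent individual rule is tied to cholangitis or colitis.

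**Working it through.** **Inputs from the documents.** Thresholds of 3, 2 and 1 subjects (stopping criteria); planned N = 30 (Study Design and Methodology); minimum N = 20 (Risk Mitigation and Alternative Strategies). The plan gives no operating characteristics for the rule, so there is no figure to reproduce.

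**Assumptions, because the documents give no rates.**

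- q: chance per subject of a worst grade of 3 or 4 for one event term, 1% to 10%.
- s: share of those events at grade 4, 10% to 30%.
- r: chance per subject of a grade 4 event of a different term, independent; 0, 2% or 5%.
- u: share of grade 4 cases not also counted at grade 3; u = 1 is worst-grade counting.
- No grade 5 events.

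**Step 1: which clusters are missed.** Let a, b and c be the numbers of subjects whose worst grade for one event is 3, 4 and 5.

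- Written rule: stop if a ≥ 3, or b ≥ 2, or c ≥ 1.
- Amended rule: stop if a + b + c ≥ 3, or b ≥ 2, or c ≥ 1.

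Enumerating every split of up to 30 subjects, the rules differ at one point only: (a, b, c) = (2, 1, 0). If a grade 4 subject is always counted as having also developed grade 3, no split is missed.

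**Step 2: probability of that cluster.** The rules differ only when a = 2, b = 1 and none of the other N − 1 subjects has a grade 4 event of another term:

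gap = C(N,2) × (N − 2) × [q(1 − s)]² × (qs) × (1 − q)^(N−3) × (1 − r)^(N−1) × u

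Worked case, N = 30, q = 3%, s = 10%, r = 0, u = 1:

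- C(30,2) × 28 = 435 × 28 = 12,180
- [0.027]² × 0.003 = 2.187 × 10⁻⁶
- 0.97²⁷ = 0.4394
- gap = 12,180 × 2.187 × 10⁻⁶ × 0.4394 = 0.0117, or 1.17 percentage points

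**Step 3: the range.** Gap in percentage points, u = 1, for s = 10% / 20% / 30%:

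| Event rate q | N = 30, r = 0 | N = 30, r = 2% | N = 30, r = 5% | N = 20, r = 0 |
|---|---|---|---|---|
| 1% | 0.08 / 0.12 / 0.14 | – | – | – |
| 2% | 0.46 / 0.72 / 0.83 | – | – | – |
| 3% | 1.17 / 1.85 / 2.12 | 0.65 / 1.03 / 1.18 | 0.26 / 0.42 / 0.48 | 0.45 / 0.70 / 0.81 |
| 5% | 3.09 / 4.88 / 5.60 | 1.72 / 2.72 / 3.12 | 0.70 / 1.10 / 1.27 | 1.45 / 2.29 / 2.63 |
| 10% | 5.74 / 9.07 / 10.41 | 3.19 / 5.05 / 5.80 | 1.30 / 2.05 / 2.35 | – |

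The r = 0 columns are upper bounds per term. Other grade 4 events help to meet the second criterion, so the gap shrinks by (1 − r)²⁹, which is 0.557 at r = 2% and 0.226 at r = 5%. If half of grade 4 cases pass through a recorded grade 3 and are counted there (u = 0.5), every figure halves.

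**Step 4: direction of the rule.** Hold q fixed, with N = 30 and r = 0, and raise the grade 4 share from 10% to 20%:

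| q | Written rule, chance of a pause | Amended rule, chance of a pause |
|---|---|---|
| 3% | 0.050 → 0.048 | 0.062 → 0.067 |
| 5% | 0.160 → 0.149 | 0.190 → 0.198 |

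Under the written rule the chance of a pause falls as events become more severe. Under the amended rule it rises.

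**The case against.** The strongest reply is that the defect depends on the reading. The criterion says that subjects develop a grade 3 event, not that grade 3 is their worst grade. A life-threatening event can fairly be taken to have crossed the grade 3 threshold, and on that reading nothing is missed. This stands as a reason for calling the point conditional. It does not remove the point, because the text does not choose between the readings, and an event first recorded at grade 4 may never have had a grade 3 entry.

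Second, the DSMB Charter is not among the documents and may define the count. That is possible. But the mandatory stop is written in the protocol, which the two sites will apply, and its wording should be sufficient on its own.

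Third, the backstops are real: 72-hour reporting, review by the monitor or IRB, the DSMB, and the individual liver rules. One more grade 3 case of that event, or one more subject with any grade 4 event, would also trigger the pause. This is accepted, and it is why the point is minor.

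Fourth, rates may be low. The section on protections against drug risks says that daily doses below 70 mg were "not associated with an increased rate of clinically relevant adverse reactions" relative to placebo. At event rates of 1–2% the gap is at most 0.1–0.8 points. That evidence comes from rheumatoid arthritis and inflammatory bowel disease over 12–13 weeks, not from PSC over six months, and the halting criteria also count disease-related events. The larger gaps do need high assumed rates. At 10% the written rule pauses the trial about half the time anyway (0.51 to 0.53 with r = 0).

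**Conclusion.** The point holds as a minor defect of wording. Under worst-grade counting, two grade 3 cases plus one grade 4 case of the same event do not pause the trial while three grade 3 cases do, and no other same-event cluster of three or more is affected. For 30 subjects and no other grade 4 events, the loss in the chance of a pause is at most about 2 points per event term at event rates up to 3%, and 3.1–5.6 points at 5%. It is smaller when other grade 4 events occur, with 20 subjects at these rates, or when some grade 4 cases are also counted at grade 3. All of these sizes rest on assumed rates. No endpoint or efficacy conclusion is affected. The case for a change is that the rule can work in the wrong direction and the correction is cheap.

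**What to change.** Reword the first criterion as: *3 subjects develop the same CTCAE event at grade 3 or higher*. Add: *each subject is counted once per event, at the worst grade reached*. Leave the counts of 3, 2 and 1 as they are. This closes the gap on either reading and gives both sites one counting rule.

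The cost is a one-line amendment, which needs IRB review and approval before use (Recruitment and Informed Consent). The downside is a slightly higher chance of a temporary pause. The increase equals the gaps tabulated above, and it arises only in the cluster of two grade 3 cases and one grade 4 case.
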